The diagnosis of AF, as well as that of other complications, is often made when the patient is symptomatic, requiring immediate and perhaps more aggressive intervention than if an earlier diagnosis had been made. Treatment is generally decided based on the size of the leak, the degree of local contamination, and the associated severity status of the patient. Thus, early diagnosis of AF by clinical, radiological and/or endoscopy is essential to provide immediate treatment through antibiotic therapy, placement of a feeding tube, application of endoscopic therapies, percutaneous drainage of collections, etc., possibly reducing the rate surgical review. For all these reasons, early prediction, diagnosis and treatment of possible major complications (Clavien-Dindo greater than 3), especially AF, are essential to improve the results and prognosis of the disease (6).

Different studies have investigated the usefulness of the use of markers, both pre and postoperative, to predict possible postoperative complications. Recent studies have evaluated different markers in early postoperative stages as predictors of AF and other major complications. These include C-reactive protein (CRP) (7), white blood cell count (RGB) (8), serum albumin (9), tumor necrosis factor  $\alpha$  (TNF  $\alpha$ ), interleukins 1 and 6, the CRP- albumin (CAR) (10-13), modified Glasgow Prognostic Score (mGPS), platelet/lymphocyte ratio and neutrophil/lymphocyte ratio (4) among others.

After carrying out a thorough bibliographic search, the small number of quality prospective studies in this area has been observed, most of them being retrospective or systematic reviews of retrospective studies.

CRP is one of the most studied inflammatory markers related to AF. It is mainly synthesized in the liver in response to proinflammatory cytokines, as an acute phase response protein, and its levels correlate with the severity of inflammation (14). CRP levels increase after surgery and commonly peak after 48 hours (15,16), subsequently decreasing in patients with an uncomplicated postoperative course. Therefore, CRP is especially valuable as a negative test, and a normal or falling CRP level on the third and fifth postoperative days (POD) can help predict which patients are not likely to develop AF (17). Although several prospective

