## OBJECTIVES

Based on the hypothesis of the study, the main and secondary objectives of this study are established:

- Main goal:

\*Design a predictive model based on clinical and analytical variables that allow identifying patients with a high risk of anastomotic leak (main variable) during the postoperative period of esophagogastric surgery.

- Secondary objectives:

\* Design a predictive model based on clinical and analytical variables that allow identifying patients at high risk of other major complications (Clavien-Dindo greater than 3) during the postoperative period of esophagogastric surgery.

\* Individually describe the postoperative evolution of the clinical and analytical parameters studied in patients without major complications or AF and those who did suffer from any of them.

\* Describe the complications and types of AF diagnosed in the study.

\* Assess the day AF was diagnosed and the treatment used for its possible resolution.

\* Assess the day AF was diagnosed and hospital stay.

\* Compare the preoperative Glasgow prognostic score (mGPS) and the biochemical value of inflammatory markers (CRP, Interleukin 6 (IL-6) and procalcitonin) and the appearance of AF.

\* Assess the AF resolution capacity of each technique used.

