## **8.2.- PARTS of the DATABASE**

After opening the REDCAP application of the AEC, you can access the data set and the different variables to be collected at each moment of the care process and which will be described in more detail below:

The main outcome variable of the study is ANASTOMOTIC LEAKAGE, a categorical variable divided into the following categories, according to the consensus definitions of the Consensus Group on Complications of Esophagectomy (ECCG) (27), which in this study will be applicable both to fistulas occurred after esophagectomy and after gastrectomy:

- NO: If this complication did not occur.
- I: Defect that does not require specific treatment or that can be treated medically or with diet modification
- II: Defect that requires some intervention, but not surgical, such as: drainage by interventional radiology, prosthesis placement, opening of the wound at the bedside, compression or wound healing.
- III: Defect requiring surgical intervention

In relation to this variable, the following data are also included in the study:

- DAY Dx LEAK (DAY of DIAGNOSIS OF THE ANASTOMOTIC LEAK: ordinal variable that shows the number of the postoperative day on which the diagnosis of the anastomotic leak occurred.
- EDA Dx LEAK (LEAK DIAGNOSIS THROUGH ENDOSCOPY): Dichotomous variable: YES/NO.
- CAT Dx LEAK (DIAGNOSIS OF LEAK BY CAT): Dichotomous variable: YES/NO.

The rest of the variables collected in this study are:

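### Resolution rates by leak-treatment technique are confounded by indication and, with the data planned, can be adjusted only in part

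*Combined protocol and SAP*

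**What the plan says.** The last secondary objective is to "Assess the AF resolution capacity of each technique used". On how techniques are chosen, the Introduction states: "Treatment is generally decided based on the size of the leak, the degree of local contamination, and the associated severity status of the patient". Section 6 (Intervention) leaves perioperative management to each center, with no common protocol.

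Section 8.2 grades the leak by what was needed to treat it:

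- Grade I: "Defect that does not require specific treatment or that can be treated medically or with diet modification"
- Grade II: "Defect that requires some intervention, but not surgical"
- Grade III: "Defect requiring surgical intervention"

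The other leak fields in that section are the day of diagnosis ("ordinal variable that shows the number of the postoperative day on which the diagnosis of the anastomotic leak occurred") and whether endoscopy or CT made the diagnosis (for example "EDA Dx LEAK (LEAK DIAGNOSIS THROUGH ENDOSCOPY): Dichotomous variable: YES/NO"). Section 8.2.4 adds one resolution field and one resolution day per patient, plus up to seven technique fields (two endoscopic, three surgical, two radiological).

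The Data analysis section directs its univariate and multivariate work at the appearance of leak and of major complications. Leak resolution is not named as an analysed outcome.

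**The concern.** Capacity is a property credited to a technique. If techniques go to systematically different leaks, the proportion resolved after each one mixes the technique's effect with the severity of the leaks it was used for. The protocol itself names the three determinants of choice, and two of them, size and contamination, are not collected. Item 1 of Limitations answers the risk of confounding by saying that the easily accessible influential variables were included; for this objective that reassurance does not hold.

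At stake is a published list of resolution rates by technique that readers would take as a ranking. A technique reserved for large or contaminated leaks would look worse than one used for small contained leaks, even if both worked equally well.

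**Working it through.** The plan gives no figure for this objective, so the check is a comparison of sections followed by an illustration.

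**Step 1: determinants of treatment against recorded fields.**

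| Determinant (Introduction) | Recorded? |
|---|---|
| Leak size | No field in 8.2 or 8.2.4 |
| Degree of local contamination | No field; nearest is non-wound surgical site infection, yes/no with its day (8.2.3) |
| Patient severity | Proxies only: ASA, ECOG and comorbidity (8.2.1); vital signs and laboratory values on days 1, 2, 3, 4 and 6 (8.2.2); Clavien-Dindo IVa/IVb, undated (8.2.3) |

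Anastomosis site and day of leak diagnosis are also available. On timing, the retrospective study of 330 patients cited in the Introduction gives a mean leak diagnosis time of 7 days, one day after the last scheduled panel. A mean does not give the share diagnosed after day 6, but many leaks may have no scheduled panel at diagnosis. Undated Clavien-Dindo grade IV may follow treatment, which makes it a weak adjuster.

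**Step 2: can the grade stand in for severity?** For surgery against no surgery it cannot: by definition, operated leaks are grade III and grades I and II contain none, so no stratum holds both. For contrasts within a modality, such as clips against endoprosthesis, grade does not define the groups, but it is still a poor adjuster. If the grade reflects the highest treatment reached, an endoscopic failure that goes to surgery moves to grade III, and the endoscopic cases left in grade II are enriched for successes.

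**Step 3: possible size of the bias.** Every input here is assumed, because the documents give neither closure rates by severity nor severity mix by technique. Let two techniques work equally well within each severity level. Then

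false gap = (severe share in A − severe share in B) × (closure in mild − closure in severe).

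| Closure mild / severe | Severe share A / B | Crude rate A / B | False gap |
|---|---|---|---|
| 90% / 80% | 60% / 30% | 84% / 87% | 0.30 × 0.10 = 3 points |
| 90% / 70% | 70% / 20% | 76% / 86% | 0.50 × 0.20 = 10 points |
| 90% / 50% | 70% / 30% | 62% / 78% | 0.40 × 0.40 = 16 points |
| 90% / 50% | 80% / 20% | 58% / 82% | 0.60 × 0.40 = 24 points |
| 95% / 60% | 80% / 10% | 67% / 91.5% | 0.70 × 0.35 = 24.5 points |
| 90% / 50% | 90% / 10% | 54% / 86% | 0.80 × 0.40 = 32 points |

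**Step 4: what a proxy would remove.** Take the 10-point case and a proxy with sensitivity and specificity of 0.75 (assumed). Among proxy-positive patients, 87.5% of A and 42.9% of B are truly severe, a gap of 0.446 × 0.20 = 8.9 points. Among proxy-negative patients the shares are 43.75% and 7.7%, a gap of 0.361 × 0.20 = 7.2 points. Weighting by the average size of the two strata, 0.475 × 8.9 + 0.525 × 7.2 = 8.0 points. Adjustment takes 10 points down to 8: it helps, but leaves most of the bias.

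**Step 5: how many leaks.** At the planned 847 patients and the 16% leak rate of the same cited study, 847 × 0.16 ≈ 136 leaks. At its 47.2% surgical share, about 64 would be operated and 72 not. Across an assumed leak rate of 5% to 34% (the Introduction quotes 0–34% after esophagectomy) the total is 42 to 288. The 847 is used here for scale only.

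**The case against.** The strongest reply is that no comparison is planned. The Objectives section uses a comparing verb for mGPS and the inflammatory markers but an assessing one here, and the Data analysis section plans no test of resolution. A descriptive table would satisfy the text. This stands: the documents do not show that the study will report surgery, or any other technique, as inferior. It does not remove the point, because the same list speaks of describing for other objectives and of capacity for this one, and nothing tells the analyst or the reader to stop at description.

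A second reply is that severity is not captured by the grade alone. This also stands. A reader might infer from the treatment-defined grade that nothing else bears on severity and that no adjustment is possible. The proxies in step 1 contradict that: partial adjustment is possible, mainly for leaks diagnosed by about day 6. Leak size remains unmeasured.

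Third, the argument about grade is complete only for surgery against no surgery. That is right, and step 2 is limited accordingly.

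Finally, it can be said that a nearer obstacle is the single resolution field set against up to seven technique fields, with no date or result for each. That is a separate problem of attribution. Solving it would leave the confounding untouched.

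**Conclusion.** The concern holds in limited form. Resolution rates by technique are confounded by indication, can be adjusted only partially with the planned data, and have no adjustment planned. The direction is against techniques used for worse leaks, provided that worse leaks close less often. The size cannot be established from the documents: 3 to 32 points is the span of assumed inputs, not an estimate, and no single value in it should be quoted as the expected bias. This is one secondary objective of a prediction study, and neither predictive model depends on it. The change is worth making because it is cheap and because leak size and degree of contamination cannot be recovered later from the database as designed.

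**What to change.** Reword the objective as: *describe the techniques used and leak resolution after each, without comparing techniques or attributing effectiveness*. This costs nothing and is sufficient on its own.

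If any comparison is wanted, add three fields for leak patients only, dated at diagnosis and completed before treatment: defect size, contained or free contamination, and organ failure yes/no. Compare techniques only with stratification or adjustment for these, and not for the leak grade. State in advance that numbers will be sparse. With size split in two, three binary fields make eight strata; 136 leaks give 136 / 8 = 17 per stratum on average, before dividing by technique (about 5 at 42 leaks, 36 at 288).

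The cost is a small extra data-entry burden for leak patients. The documents do not say whether size and containment are routinely reported at every center, so the fields need a not-available option.

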## MATERIAL AND METHODS

The methodological properties of the study are described below:

### 1.- Type of design

Prospective and multicenter study that aims to develop, with the help of artificial intelligence methods, a tool and predictive model that allows identifying cases with a high risk of anastomotic leak and/or major complications through the analysis of different clinical and analytical variables collected during the postoperative period. of patients undergoing esophagectomy or gastrectomy.

### 2.- Study population

Patients diagnosed with neoplasia of the esophagus or stomach with an indication for oncological surgery with curative intent in any of the centers participating in the study.

### 3.- Inclusion and exclusion criteria

Patients with a surgical indication and curative intent due to esophagogastric neoplasia who do not meet exclusion criteria and recruited by hospitals nationwide that decide to participate in the study will be included.

The study exclusion criteria are:

- Patients under 18 or over 85 years
- Patients with chronic infections
- Patients with synchronous tumors in other locations
- Patients with autoimmune disease
- Patients who die in the operating room
- Patients who do not sign the informed consent to participate in the study
- Patients in clinical stage IVB
- Surgical resection R2 (there are macroscopic remains of the tumor in the surgical field after performing the resection of the surgical piece)
- Combined intraoperative resection of other organs
- Surgeries without anastomosis

In addition, the following situations are considered criteria for abandonment or withdrawal of the patient from the study:

- Revocation of the informed consent expressed by the patient at any time during the study.
- Patient loss during study follow-up
- Incorrect data collection according to the indications provided

### 4.- Sample size

The purpose of the study is to recruit as many patients as possible from all national centers who wish to participate.

For an alpha error of 5% (95% confidence) with a precision of 3% and estimating a number of patients with major complications (including AF) around 30%, the calculation of the sample size yields a total of 847 patients. However, the final sample size may be smaller depending on the proportion of complications detected and the statistical and artificial intelligence models to create the predictive model will be adapted to the event rate provided by the recruited sample.

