## SUMMARY

In esophagogastric surgery, the appearance of a leak at the level of the anastomosis is the most feared complication with important repercussions for both the patient and his disease. There are many risk factors that are related to its appearance and that makes it difficult to prevent its appearance. Making an early diagnosis of it is important for optimal management and resolution and therefore, different studies have investigated the usefulness of the use of markers, both pre and postoperative, to predict possible postoperative complications such as anastomotic leak. Due to the importance of early diagnosis and management of possible complications after esophagogastric surgery, it is mandatory to research and create predictive models that identify patients with a high risk of suffering complications, in order to be able to act accordingly. indicating the complementary examinations that are considered adequate to obtain an early diagnosis.

The PROFUGO study (PRedictive Model for the Early Diagnosis of Anastomotic LEAK after esophagectomy and gastrectomy) is proposed as a prospective and multicenter study at the national level that aims to develop, with the help of artificial intelligence methods, a tool and predictive model that allows identifying cases with a high risk of anastomotic leak and/or major complications through the analysis of different clinical and analytical variables collected during the postoperative period of patients undergoing esophagectomy or gastrectomy.

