## INTRODUCTION

Esophageal cancer is the sixth leading cause of cancer death worldwide, with an incidence that has been increasing in recent years. Surgery is the mainstay of curative therapy for fit patients with the ability to tolerate extensive surgical procedures. Postoperative morbidity associated with esophagectomy is high (around 60%) (1), pulmonary complications occur in 20-50% of patients, and anastomotic leak (AF) has a variable incidence depending on the series (0- 34%) (1, 2) with an associated mortality of 5-36% (3). Regarding gastric cancer, it represents the fifth most common and the second most frequent cause of death from cancer worldwide, with a rate of postoperative complications close to 40-50% (4).

Among the postoperative complications, AF is the most feared, presenting a high mortality rate. This complication is not only associated with a longer hospital stay and increased costs, but also with a worse prognosis of the disease and the patient's quality of life (5). The variability in the rate of AF in the literature is due to the lack of a precise definition that is generally accepted by all groups, as well as the need to establish a reliable and unanimous diagnostic method. In addition to possible technical failures, there are many potential risk factors that may be related to the appearance of this complication. Thus, patients with this type of pathology and due to factors such as accelerated metabolism and decreased intake present a high risk of malnutrition, hypoproteinemia and systemic inflammation, which can alter collagen synthesis, reduce tensile strength in the anastomosis, facilitate poor tissue healing and induce anastomotic dehiscence.

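### The stated inputs give 897 patients, not 847, and the figure is the precision of the composite complication rate; it does not size the leak model (minor)

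*Combined protocol and SAP*

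**What the plan says.** Section 4 (Sample size) under Material and Methods opens by aiming for the largest recruitment that the participating centres can deliver. It then gives a calculation at 5% alpha (95% confidence) "with a precision of 3% and estimating a number of patients with major complications (including AF) around 30" per cent, and reports that "the calculation of the sample size yields a total of 847 patients". It states no formula, population size, dropout allowance or expected number of leaks. It adds that the final number may be lower, and that the models "will be adapted to the event rate provided by the recruited sample".

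The Objectives section makes the main goal a model based on variables that "allow identifying patients with a high risk of anastomotic leak (main variable) during the postoperative period of esophagogastric surgery". A model for other major complications is a secondary objective. Section 8.2 agrees: "The main outcome variable of the study is ANASTOMOTIC LEAKAGE, a categorical variable divided into the following categories". Section 1 (Type of design) puts the aim more broadly, as a tool that "allows identifying cases with a high risk of anastomotic leak and/or major complications".

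Enrolment is set by time. Under Stages of Development, sections 3 (Duration of the study) and 5 (Schedule) have each centre include consecutive patients for one year.

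**The concern.** There are two points. First, the inputs in section 4 are those of the usual formula for estimating one proportion, and that formula does not return 847 at a rate of 30%. This is the study's only planning figure, and a reader cannot reproduce it from the text. Second, the proportion in the calculation is major complications with leak included, while the main objective and main outcome are leak alone. Knowing a composite rate to within 3 points says nothing about how large a model for leak can be. The section does not say that its figure leaves that question open.

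**Working it through.** **Inputs, all from section 4 (Sample size):** two-sided 95% confidence, z = 1.96; half-width d = 0.03, read as absolute; proportion p = 0.30; stated total 847.

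**1. The plan's own figure.** n = z² p(1−p) / d² = 3.8416 × 0.30 × 0.70 / 0.0009 = 896.4, rounded up to **897**. The stated 847 is not reproduced. The gap is 897 − 847 = 50 patients, which is 5.9% of 847.

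**2. What 847 delivers.** Half-width = 1.96 × √(0.21 / 847) = 0.0309, or **±3.09%**. At 897 it is 1.96 × √(0.21 / 897) = 0.0300.

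**3. Other methods with the same inputs.**

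| Variant (p = 0.30, d = 0.03) | n |
|---|---|
| Wilson | 894 |
| Agresti-Coull | 894 |
| Arcsine | 896 |
| Exact binomial | 928 |
| Continuity-corrected Wald | 930 |
| z = 2 instead of 1.96 | 934 |
| 90% confidence | 632 |
| 99% confidence | 1549 |

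None is close to 847. A dropout allowance moves the figure further away: with 10%, 897 / 0.90 = 996.7, so 997.

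**4. What would give 847.** Each of these needs an input that the section does not state:

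- A different rate: p(1−p) = 847 × 0.0009 / 3.8416 = 0.1984, so p = 0.273, or about 27.3%.
- A finite-population correction, n / (1 + (n−1)/N): with N = 15,400, 896.4 / (1 + 895.4 / 15,400) = 847.1. N is therefore about 15,400.
- A confidence level of about 94.3%.

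**5. How much a rounded rate can cover.** If 30% stands for any value from 27.5% to 32.5%, n runs from 852 to 937, which just misses 847. If it stands for 25% to 35%, n runs from 801 to 972, which contains 847.

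**6. What the figure describes.** The proportion in the formula is the composite. No leak rate enters it, and section 4 gives no expected leak rate or leak count. The Introduction offers background only. It says that "anastomotic leak (AF) has a variable incidence depending on the series", with a range of 0–34% for esophagectomy; at 847 patients that is 0 to 0.34 × 847 = 288 leaks. One cited retrospective study of 330 patients reports 16%. Used purely as an illustration, that gives 0.16 × 847 = 135.5, about 136 leaks.

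**The case against.** **The rate is only approximate.** The section qualifies its 30%, and a true input near 27.3% reproduces 847. This stands in part. The 27.5–32.5% band is one rounding convention among several, and the wider 25–35% band does contain 847. A reader might infer that 847 cannot be reconciled with the text at all. That is too strong, because a very loose reading of the qualifier could cover it. But 27.3% cannot be recovered from what is printed, so the point is confined to the inputs as stated.

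**The section already names its quantity.** This largely stands. It gives both the proportion estimated and the precision target, so it would be wrong to say that the figure has no declared purpose. It also keeps the figure apart from the modelling by leaving the models to follow the observed event rate. What is missing is a plain statement that the figure does not size the leak model.

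**The composite belongs to the study's aim.** This also stands. The Summary and the design section both include major complications. Estimating that rate is legitimate, but it is not the main outcome.

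**Nothing depends on the number.** This stands too, and it is why the point is minor. Recruitment is one year of consecutive patients per centre, and a smaller final sample is allowed.

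**Conclusion.** The figure is wrong as written, and the matter is minor. With a rate of 30%, an absolute half-width of 3 points, two-sided 95% confidence and no finite-population correction, the requirement is 897. The stated 847 gives ±3.09%, a loss of 0.09 percentage points. If the sponsor used another rate or a finite population, 847 may be right for those inputs, but the protocol does not state them.

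The figure is the precision of the composite rate and does not size the leak model. A reader might infer from this that 847 is too few, or that the leak model is underpowered. The documents do not support that. They give no expected leak rate for this mixed esophagectomy and gastrectomy cohort and no size criterion for the model. The background range of 0–34% is too wide to settle the question, and the 16% from one study is only an illustration.

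**What to change.** In section 4 (Sample size), do one of the following:

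- state 897 patients for ±3%;
- keep 847 and state ±3.1%;
- if another rate or a finite population was in fact used, state it in place of the present inputs.

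In each case, add one sentence saying that the figure refers to the composite rate of major complications only and does not size the prediction model for leak.

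This is a wording change. Enrolment and analysis stay as they are. The only cost is a slightly less favourable stated precision if 847 is kept. The sponsor may also wish to state an expected leak rate and say how the leak model's size will follow from the leaks observed. That is optional and not part of this correction.
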